Statistical methods:	
A separate, detailed statistical analysis plan (SAP) will be finalized prior to locking the database. All analyses of safety and efficacy for this study will be descriptive in nature and presented by group. Subject demographics and baseline characteristics will be summarized. Subject data listings will also be provided.
 
Summaries for quantitative variables will include the mean, median, standard error, minimum, and maximum. For qualitative variables, the summaries will include the number and percentage of subjects for each outcome, and the 95% CI, when

Protocol for clinical study of Brequinar

Protocol No.: 21-VIN-0372

Version No.: 2.1; Dated: 29 Dec 2021

Supersedes: 02; Date of Supersedes: 30 Sep 2021

	
appropriate. Any statistical testing will be considered exploratory and descriptive. All computations will be performed using SAS® (Version 9.4 or higher). Safety and tolerability will be assessed in terms of AEs, SAEs, and safety laboratory data.
 
Adverse event data will be descriptively evaluated. All AEs will be reported in data listings. The incidence of treatment-emergent adverse events, defined as TEAEs occurring after first dose will be tabulated by Medical Dictionary for Regulatory Activities (MedDRA) preferred term and system organ class, and by severity and relationship to study treatment. All laboratory results and other clinical measures will be summarized using appropriate descriptive statistics.

Ethical Issues:	
The study will commence only after a written approval is obtained from the Institutional Ethics Committee and applicable regulatory authorities. The trial will be conducted as per the biomedical research on human participants (ICMR) 2017 guidelines, New Drugs and Clinical Trial Rules (2019) of India, ICH (Step 5 'Guidance on Good Clinical Practice' ICH Guidance E6 (R2), Declaration of Helsinki (Brazil, 2013) and with procedures oriented to Good Laboratory Practice and applicable regulatory guidelines.

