7.0 STUDY ENDPOINTS

Primary Endpoints:

- Frequencies of grade 3 and 4 toxicities and serious adverse events (SAEs) considered by the investigator to be related to the combination, brequinar alone or placebo alone.

Secondary Endpoints:

- qPCR SARS-CoV-2 levels through Day 29 and at days 4, 8, 12, 15, 22, and 29;
- Time to symptom improvement through Day 29;
- Percentage of subjects requiring hospital admission/re-admission as an in-patient for >24 hours through Day 29;
- Percentage of subjects requiring medical attended visits, e.g., hospitalization, emergency room visits, Urgent Care/Family Doctor visits through Day 29;
- Percentage of subjects requiring supplemental support such as oxygen through Day 29.

Exploratory Endpoints (PK):

- Analysis of brequinar's pharmacokinetic profile in a subset of patients that have received brequinar as a part of therapy and have consented to provide PK samples.

Clinical improvement will be defined as a 2-point or greater improvement on an 8-point WHO ordinal scale in every subject measured on each designated day, from the date of randomization through day 29. This scale has been used in the current COVID-19 outbreak.

Ordinal Scale for Clinical Improvement

Patient State	Descriptor	Score
Uninfected	No clinical or virological evidence of infection	0
Ambulatory	No limitation of activities	1
	Limitation of activities	2
Hospitalized	Hospitalized, no oxygen therapy	3

Protocol for clinical study of Brequinar

Protocol No.: 21-VIN-0372

Version No.: 2.1; Dated: 29 Dec 2021

Supersedes: 02; Date of Supersedes: 30 Sep 2021

Mild disease	Oxygen by mask or nasal prongs	4
Hospitalized	Non-invasive ventilation or high-flow oxygen	5
Severe Disease	Intubation and mechanical ventilation	6
	Ventilation + additional organ support – pressors, RRT, ECMO	7
Dead	Death	8

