9.7 Patient identification and Randomisation

Randomization will be carried out using SAS® (SAS Institute Inc., USA) version 9.4 or higher. Randomization will be done in blocks using PROC PLAN such that the design is unstructured. The treatment allocation will be determined according to the randomization schedule and randomization schedule will be done per cohort.

Screening and Randomization Numbering

Each subject will be assigned a unique number that will serve to identify laboratory specimens and all documents, and if randomized throughout the study. If a subject fails to qualify for allocation to the study i.e. is a screen failure, the subject's unique number will not be used for another subject.

Screening number will be a combination of center number, project number and subject number. The center number will be assigned by Veeda to the investigative site (e.g. A, B, C, D) and subsequent sites are assigned consecutive alphabet numbers. Upon signing the informed consent form, the subject will be assigned a screening number by the Investigator. At each site the first subject consented is assigned screening number e.g. A-21-0372-001, and subsequent subjects are assigned consecutive numbers (e.g., the second subject consented is assigned screening number A-21-0372-002, the third subject is assigned screening number A-21-0372-003). Once a screening number is assigned to a subject, that number will not be reused.

If the subject is deemed eligible for enrollment into the study and will commence dosing, then a randomization number will be assigned via IWRS as defined in the randomization plan. Subjects will be randomized with the next qualifying subject given the next available randomization number.

A source document maintained at the site will link the screening number to the randomization assignment number (once assigned) and the same will be reflected in screening and enrollment log of Investigator site file.

The assigned subject number will be recorded in the CRF of the subject.

Protocol for clinical study of Brequinar

Protocol No.: 21-VIN-0372

Version No.: 2.1; Dated: 29 Dec 2021

Supersedes: 02; Date of Supersedes: 30 Sep 2021

The personnel involved in dispensing of study drug and verification of dispensed study drugs will be accountable for ensuring compliance to randomization schedule.

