15.2 Sample Size Estimation

There is no prospective powering in this study. The sample size was chosen to provide an adequate number of subjects to provide reasonable safety and efficacy data for this type of study.

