15.4 Analysis of Efficacy Data

All statistical analysis will be done using SAS® Version 9.4 or higher (SAS Institute Inc., USA).

For continuous variables, the summary statistics will be the number of observations, mean, standard deviation, median, minimum and maximum values. Categorical values will be summarized using frequencies and percentages.

Primary Endpoints:

- Frequencies of grade 3 and 4 toxicities and serious adverse events (SAEs) considered by the investigator to be related to the combination, brequinar alone or placebo alone.

Because the primary study endpoint is a safety parameter no formal statistical testing will be performed for this parameter.

Protocol for clinical study of Brequinar
 Protocol No.: 21-VIN-0372
 Version No.: 2.1; Dated: 29 Dec 2021
 Supersedes: 02; Date of Supersedes: 30 Sep 2021

Secondary Endpoints:

For subjects treated with the brequinar-dipyridamole combination compared to subjects treated with the brequinar and to subjects treated with the placebo combination through Day 29, to determine:

- SARS-CoV-2 levels through Day 29 and at days 4, 8, 12, 15, 22, and 29 will be analyzed using analysis of covariance (ANCOVA) test;
- Time to symptom improvement through Day 29 will be analyzed using Kaplan-Meier time-to-event analysis;
- Percentage of subjects requiring hospital admission/re-admission as an in-patient for >24 hours through Day 29 will be analyzed using Fisher exact / chi square test;
- Percentage of subjects requiring medical attended visits, e.g., hospitalization, emergency room visits, Urgent Care/Family Doctor visits through Day 29 will be analyzed using Fisher exact / chi square test ;
- Percentage of subjects requiring supplemental support such as oxygen through Day 29 will be analyzed using Fisher exact / chi square test.

Exploratory Endpoints:

- Brequinar's pharmacokinetic profile in a subset of patients that have received brequinar as a part of therapy and have consented to provide PK samples will be analyzed descriptively.

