15.5 Safety Analysis

All safety analysis will be conducted using the safety population set.

Frequency distribution or summary statistics of all demographics variable and baseline characteristics will be generated by treatment arm.

The evaluation of the drug safety will be based on clinical AEs, vital signs, physical examination, concomitant medications and laboratory abnormalities reported during the study and incidence of adverse events and treatment emergent adverse events in each arm during the study. All safety presentations will include subjects who receive at least one dose of the study medication and will group subjects by treatment received. Frequency distributions and individual listings of all adverse events will be generated. Changes in clinical laboratory test results from baseline will be listed.

A treatment emergent adverse event is defined as any event not present prior to the initiation of the treatments or any event already present that worsens in either intensity or frequency following exposure to the treatments.

Adverse events will be coded using Medical Dictionary for Regulatory Activities (MedDRA) terms using the version that is current at the time the first subjects is enrolled and will be summarized by system organ class (SOC) and preferred term within SOC. The Common Terminology Criteria for Adverse Events CTCAE 5.0 will be used to grade the severity of adverse events.

Protocol for clinical study of Brequinar

Protocol No.: 21-VIN-0372

Version No.: 2.1; Dated: 29 Dec 2021

Supersedes: 02; Date of Supersedes: 30 Sep 2021

Adverse Events will be summarized by treatment and overall. AE summary tables will include counts of subjects and the number of events. If a subject experiences more than one episode of a particular AE, that subject will be counted only once for that event. If a subject has more than one AE that coded to the same preferred term, the subject will be counted only once for that preferred term. Similarly, if a subject has more than one AE within a SOC, the subject will be counted only once in that SOC.

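### The final analysis is set out by regimen with no dose or cohort term, although randomisation is by dose cohort and the expansion has no placebo

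*Combined protocol and SAP*

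**What the plan says.** All references are to protocol Version 2.1.

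- **Primary endpoint (Section 7, repeated in 15.4):** frequencies of grade 3 and 4 toxicities and SAEs "considered by the investigator to be related to the combination, brequinar alone or placebo alone". Section 15.4 adds: "Because the primary study endpoint is a safety parameter no formal statistical testing will be performed for this parameter".
- **Secondary endpoints (15.4):** "For subjects treated with the brequinar-dipyridamole combination compared to subjects treated with the brequinar and to subjects treated with the placebo combination". Viral load is analysed by ANCOVA and time to symptom improvement by Kaplan-Meier. Neither has a dose or cohort term.
- **Safety (15.5):** "Adverse Events will be summarized by treatment and overall"; safety presentations "will group subjects by treatment received".
- **Synopsis, statistical methods:** "All analyses of safety and efficacy for this study will be descriptive in nature and presented by group".
- **Randomisation (9.7):** "randomization schedule will be done per cohort".
- **Design (9.1):** four Part 1 cohorts at 50, 100, 150 and 200 mg brequinar, each with 8 combination, 4 brequinar and 4 placebo subjects. The expansion of about 48 is at the highest dose that meets the safety criteria: about 32 combination, 16 brequinar, no placebo.
- **Sample size (15.2):** "There is no prospective powering in this study".

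**The concern.** A multi-dose trial of a combination not previously given in the clinic should report what was seen at each dose. Section 5.5 itself links the most common brequinar side effects in cancer patients to higher doses. Read literally, the analysis sections yield one frequency for the combination across a fourfold dose range, and one efficacy contrast averaged over doses.

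The expansion adds a second difficulty. It enlarges two of the three regimens, at one dose and in a later period. A three-group comparison that ignores cohort therefore sets combination subjects from both periods against placebo subjects from the first period only. That gives up, for the placebo contrast, the balance that randomising within cohorts had secured.

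**Working it through.** **1. The plan's own figures.** Part 1: 4 × (8 + 4 + 4) = 64, as stated. Expansion: 32 + 16 = 48, as stated. Total: 64 + 48 = 112.

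**2. Row sizes if pooled over dose.** This assumes that all four cohorts fill.

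| Regimen | Part 1 | Expansion | Row | At expanded dose | At each other dose |
|---|---|---|---|---|---|
| Combination | 32 | 32 | 64 | 40/64 = 62.5% | 8/64 = 12.5% |
| Brequinar | 16 | 16 | 32 | 20/32 = 62.5% | 4/32 = 12.5% |
| Placebo | 16 | 0 | 16 | – | – |

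The shares are the same whether the expansion is at 200 mg or, after a failed fourth cohort, at 150 mg. An early-stopped cohort would shrink the denominators slightly. A pooled row is therefore dominated by one dose and is not an even average.

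**3. Enrolment period.** Suppose outcomes shift by δ, equally in every regimen, between Part 1 and the expansion.

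- Combination minus placebo, all subjects: (32/64)δ − (0/16)δ = 0.5δ.
- Combination minus brequinar, all subjects: (32/64)δ − (16/32)δ = 0.
- Any contrast within Part 1: 0, because every cohort is 2:1:1.

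Only the full-row placebo contrast is distorted. Combination versus brequinar keeps 2:1 at every dose and in both periods, so pooling averages it over doses without confounding it.

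**4. Averaging over doses.** Let D be the effect at an active dose; activity by dose is an assumption, since the documents give none for this combination.

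- One inactive 8-subject dose: 24/32 = 0.75D in Part 1; 56/64 = 0.875D on the full row.
- Only the expanded dose active: 8/32 = 0.25D in Part 1; 40/64 = 0.625D on the full row.

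**5. Is toxicity reviewed by dose during the trial?** Yes. Section 12.9 allows no related grade 3 or higher toxicity if a cohort is to be declared safe. With a true rate p among the 8 combination subjects, the chance that the cohort fails this condition is 1 − (1 − p)^8: 57% at p = 10%, 83% at 20%, 90% at 25%, 94% at 30%. The rates are assumed.

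**6. Precision of the split rows.** With zero events, the exact 95% upper limit is 1 − 0.025^(1/n): 60.2% for n = 4, 36.9% for n = 8, 8.8% for n = 40. For the pooled n = 64 it is 5.6%.

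**The case against.** Four points are made on the other side, and much of them stands.

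**Pooling is not stated.** A reader might infer that the protocol prescribes pooling over dose. It does not. The terms treatment, arm and group are undefined, arms are numbered within each cohort with their dose, and Section 15.1 defers methods and mock tables to a SAP whose text is not in these documents. Pooling is the natural reading of the three-regimen wording, but it remains an inference. The point that survives is that no analysis section provides a dose or cohort term, or says how the expansion joins Part 1.

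**Toxicity is monitored by dose.** A reader might also infer that a toxic dose would be hidden. The documents do not support that. An unblinded physician judges each cohort against set criteria, cohort stopping rules apply, the DSMB meets before the expansion, cohort safety data go to regulators, and individual adverse event listings are produced. These are decisions and listings, however, not reported frequencies. The cohort judgement is made on Day 15 results while follow-up runs to Day 29, and the cohort stopping rule is worded for the period before 16 subjects are complete, so it does not expressly cover the expansion.

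**Inactivity at low dose is unproven.** The outpatient study CRISIS-02 found no statistically significant difference from placebo in viral load with brequinar alone. That does not show that 50 mg with dipyridamole is inactive, so step 4 only illustrates averaging.

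**The study is unpowered and exploratory.** This is true, and cells of 8 and 4 support little inference. It argues for descriptive labelling, not for leaving dose out.

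**Conclusion.** The point holds in a limited form. Sections 7, 15.4 and 15.5 specify results by regimen only, while the design randomises within dose cohorts and then expands one dose without placebo. A toxic dose would still be visible to those running the trial. What is missing is a specified dose-level frequency for the primary endpoint in the final report, any dose-level step for viral load or symptoms, and a rule for combining the expansion with Part 1.

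If the regimens are pooled, which the text suggests without saying so, and all cohorts fill, 62.5% of the combination row is at one dose and the placebo contrast carries half of any shift between periods. The size of such a shift is unknown. Combination versus brequinar would be averaged over doses but not biased by period under step 3. Because the study is descriptive, this is a cheap improvement that should be made and not a flaw that invalidates the trial.

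**What to change.** **Section 15.4.**
- Include cohort as a stratum in the viral-load ANCOVA and in the time-to-improvement analysis (for example, a stratified log-rank test beside the Kaplan-Meier curves).
- Make the expansion its own stratum, informing combination versus brequinar only.
- Base placebo contrasts on Part 1: 32 combination and 16 brequinar against 16 placebo if all cohorts fill. State this explicitly, because a single model with common treatment effects would otherwise let the expansion inform the placebo contrast indirectly through brequinar.

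**Section 15.5.**
- Report the primary endpoint and adverse events by regimen and dose, with exact 95% intervals, beside the pooled rows. Pool placebo across the Part 1 cohorts.
- Label between-dose comparisons as descriptive and non-randomised, since each cohort opens only after the previous dose has met the safety criteria.

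An ordered-dose term for viral load is optional; it would rest on the same sequential cohorts.

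**Cost.** Protocol or SAP wording and extra table columns, with no change to conduct or sample size. The drawback is small cells (8 and 4 at each non-expanded dose) with wide intervals. Placebo contrasts give up the 32 expansion combination subjects, who have no concurrent placebo. The rule is best fixed now, since Section 15.1 requires the SAP only before database lock, by which time cohort results will have been reviewed unblinded.

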16.0 AMENDMENT TO THE PROTOCOL

Any significant change in the study procedure or study design will only be effected upon mutual agreement between the Sponsor, CRO and Investigator and after obtaining a favorable opinion from the Ethics Committee and regulatory authority(ies). All such changes will be documented in the amended version of the protocol and a list of changes with reference to the previous version will be generated and submitted to the IEC and regulatory authorities as soon as possible. In cases where there is an immediate safety hazard to the subjects, the amended protocol will be effective immediately and approval of the IEC will be obtained as soon as possible.

17.0 SOURCE DATA ACCESSIBILITY

Quality Assurance (QA) auditors and study monitors of Veeda Clinical Research Ltd. as well as sponsor's monitors, IEC and Regulatory agency(ies) will have access to raw data during inspection and audits.

18.0 STUDY MONITORING

Monitoring procedures developed by Veeda will be followed in order to comply with GCP guidelines and to ensure acceptability of the study data for national registration purposes. During the course of the study, a monitor from Veeda will perform site visits to review protocol compliance, compare CRFs to individual subject's medical records, assess drug accountability, and ensure that the study is being conducted according to pertinent regulatory requirements. CRF entries will be verified with source documentation.

The Sponsor or its representative may visit the study facilities at any time in order to maintain current and personal knowledge of the study through review of the records, comparison with source documents, observation and discussion of the conduct and progress of the study.

This clinical trial is to be conducted at Investigator sites and the Investigators should permit the different stakeholders for monitoring/ auditing/ inspections at their site.

19.0 QUALITY CONTROL AND QUALITY ASSURANCE AUDITS

Auditing procedures developed by Veeda will be followed in order to comply with GCP guidelines and to ensure accuracy, completeness and authenticity of the data generated, recorded and reported and acceptability of the study data for international registration purposes.

The raw data generated during the course of the study as well as reports will undergo a random quality assurance process for conformance to this protocol and all the governing SOPs by the Monitors and the auditors of Veeda Clinical Research Ltd, respectively. The final report will contain a statement of quality assurance duly signed

Protocol for clinical study of Brequinar
 Protocol No.: 21-VIN-0372
 Version No.: 2.1; Dated: 29 Dec 2021
 Supersedes: 02; Date of Supersedes: 30 Sep 2021
 by the Head, Quality Assurance department.

20.0 ETHICS

20.1 Ethics Committee

This protocol and corresponding informed consent Document (ICD) (containing information about the study to be given to subjects) to be used to obtain written informed consent of study subjects will be reviewed by IEC and subjects will not be enrolled into the study until IEC approves the protocol and ICD.

The study will be conducted according to the current version of the IEC approved protocol, Relevant SOPs, [New Drugs & Clinical Trial Rules, 2019 of CDSCO (Central Drugs Standard Control Organization), Ministry of health and family welfare, Government of India], [Ethical guidelines for biomedical research on human participants, ICMR (Indian Council of Medical Research (2006)], [ICH (The International Council for Harmonization of Technical Requirements for Pharmaceuticals for Human Use) E6 (R2) 'Guideline for Good Clinical Practice' 2016], Declaration of Helsinki – Brazil, October 2013].

20.2 Written Informed Consent

Investigator or designated study personnel before initiation of any study related procedure will inform the subject (in a language best understood by the subject) through an oral presentation regarding the purpose, procedures to be carried out, information on the investigational medicinal products, potential hazards, benefits and rights of the study subjects with maintaining adequate social distancing. Subjects will be encouraged to ask questions and clarify their doubts regarding any aspect of the study and the same would be documented in the source notes with sign and date. The ample time after completion of ICF discussion will be given to the subjects to think and take an informed and voluntary decision. Investigator will ensure that the entire process of informed consent is followed as per local regulatory requirement for each subject at the respective site maintaining the confidentiality of subject's personal information and all relevant records will be maintained in source file. The responsibility for taking informed consent must remain with that of a medically qualified person and cannot be delegated to a non-medically qualified person.

Subject (or legally acceptable representative) should be present during the entire informed consent process and will also append his/her signatures on the informed consent form. If subject or subject's legally acceptable representative is unable to read/write, an impartial witness should be present during the entire informed consent process, and will append his/her signatures on the informed consent form. In both the above cases, subjects will be required to give a thumb impression on the informed consent form. Only those subjects who are able to understand the ICF and able to communicate with the study personnel will be enrolled in the study.

The subjects will give their written consent for participation in the trial by signing or by putting a thumb impression on the informed consent form, which will also be signed by the Investigator or his/her designate.

If any new information becomes available during the course of the study that may be relevant to the subject's willingness to continue participating in the trial, the Investigator must inform the subject in a timely manner,

Protocol for clinical study of Brequinar

Protocol No.: 21-VIN-0372

Version No.: 2.1; Dated: 29 Dec 2021

Supersedes: 02; Date of Supersedes: 30 Sep 2021

and a revised written informed consent must be obtained.

Investigator will ensure that all the subject are handed over a signed and dated copy of the informed consent form immediately once the informed consent process is completed.

